### Setting

Patients who are able to comply with the requirement of radioiodine therapy and consented to participate in this trial will be given appropriate counselling. These patients will be screened for inclusion and exclusion criteria. A written informed consent will be obtained and patients will then be recruited into this study.

Once recruited, history, physical examination including baseline eye examination for possible Thyroid Eye Disease (TED) will be carried out. *TED* as defined according to the presence of eye signs in categories 2–6 of the NOSPECS classification and determined clinical activity score of thyroid eye disease according to EUGOGO criteria.

Patients will be then assessed for baseline thyroid function test (TFT), renal profile (RP) and liver function test (LFT) during screening. Patients will receive either lithium carbonate 300mg once daily or carbimazole 10mg once daily, which is the current standard therapy. The necessary precautions will be given with regards to the study drugs.

Patients will be enquired of any possible side effects during the clinic visits. Lithium levels will be checked at week 1 and at the end of 2 months of initiation (refer study flow chart). If patient develops intolerable side effects or the lithium level exceeded therapeutic range, the confounding drug will be stopped and patient will be managed accordingly. The patient will subsequently be withdrawn from the study. It is important to note that the lithium dose used in this study is of low dose, hence the side effects risks anticipated would be low.

Current waiting period in PPUKM is about 2months. Patients will be on the above treatment for a duration of 2 months and carbimazole will be stopped 3 days prior to radioactive iodine treatment. RAI will be administered at a fixed dose of 15mCi in both groups. Bloods will be drawn for TFT, RP, LFT and lithium level on the RAI day. Lithium will be discontinued on day 3 post RAI. The timeline for stopping both the carbimazole and lithium are as per clinical practice guidelines. Patients will be followed up at months 1, 3 and 6 post RAI with TFT during each visit.

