### *Definition of cure*

Cure is defined as achievement of euthyroidism or hypothyroidism at 6 months after radioactive iodine therapy. Euthyroidism is defined as having serum TSH and Free T4 level within normal range without anti thyroid drug. Hypothyroidism is defined as having elevated TSH with low or normal free T4 level or requiring thyroxine replacement.

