## Refusals, withdrawals, lost to follow-up

Patients can withdraw themselves from the study at any point of time. If patient had changed the decision and opted out of radioactive iodine, endocrinologist should be contacted immediately and clinic visits will be arranged to review the patient. If patients were lost to follow-up, weekly phone calls will be made on 4 consecutive weeks. Patients may be withdrawn if the investigator deems that it is detrimental or risky for the patient to continue. Follow up visits at endocrine clinic will be arranged for all withdrawn patients. Withdrawn subjects will not be replaced

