#### **Detecting and documenting AE**

- Information about all AEs, whether volunteered by the patient, discovered by investigator questioning or detected through physical examination, laboratory test or other means, would be documented on the Adverse Event Form and followed up as appropriate. The AE form should be emailed to the coordinating investigator [name] [name] at [contact].

- When eliciting experiences of AE from a subject, ask a standard non-leading question like "Do you feel different in any way since starting the new treatment/the last visit?" This question will be put to the subject in his/her own language at each study visit.

- Each AE should be described by:

Nature of AE

- This should be documented in terms of a medical diagnosis(es). When this is not possible, the AE should be documented in terms of signs and/or symptoms observed by the investigator or reported by the subject.

Duration:

- Start and end dates

Assessment of causality:

The investigator should attempt to explain each AE and assess its relationship, if any, to the study treatment. Causality should be assessed using the following definitions:

- Very likely
  - The AE follows a reasonable temporal sequence from study treatment administration
  - Abates upon discontinuation of study treatment
  - Reappears on repeated exposure (re-challenge)
- Probable
  - The AE follows a reasonable temporal sequence from study treatment administration
  - Abates upon discontinuation of study treatment
  - Cannot reasonably be explained by known characteristics of the subject's clinical state
- Possible
  - The AE follows a reasonable temporal sequence from study treatment administration.
  - But could have been produced by the subject's clinical state or other mode of therapy administered to the subject
- Doubtful
  - The temporal association between study treatment and AE is such that the study treatment is not likely to have any reasonable association with the observed event
- Very unlikely
  - The AE is definitely produced by the subject's clinical state or other mode of therapy administered to the subject

The degree of certainty with which an AE is attributed to study treatment or alternative cause like natural history of disease or concomitant treatment should be guided by the following considerations:

- Time relationship between treatment and occurrence of AE
- De-challenge and re-challenge information, if applicable
- Known pharmacology of the drug

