## Study Visits and Procedures

Time line	Carbimazole arm	Lithium arm
0 (recruitment)	History, physical examination including baseline eye examination for possible thyroid eye disease will be carried out. 10mls blood will be drawn for baseline TFT, RP) and LFT.	
1 week later	-	Patients will be inquired of any possible side effects. 4mls blood will be drawn for lithium level and RP
2 months later (on RAI day)	History and Physical Examination and 8mls of blood drawn for TFT, RP, LFT	History and Physical Examination and 10mls of blood drawn for TFT, RP, LFT and TDM lithium. Patients will be inquired of any possible side effects.
1 months after RAI	History and Physical Examination and 2mls of blood drawn for TFT	
3 months after RAI	History and Physical Examination and 2mls of blood drawn for TFT	
6 months after RAI	History and Physical Examination and 2mls of blood drawn for TFT	

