### Risk Benefit Assessment

There is minimal risk for this study as the treatment of these patients are in accordance to standards of care. Study findings shall potentially greatly improve treatment outcomes. The expected benefit outweighs the risk to the participants and thus this study should be supported. This study examines patient-outcomes and results will be beneficial for policy makers to plan and structure comprehensive care and tailor it to best suit the patients. If patient develops intolerable side effects or lithium level above therapeutic range, the confounding drug will be stopped and will be managed accordingly. The patient will be excluded from this study.

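### Stopping study drug for side effects or a high lithium level also ends study participation, and nothing says 6-month cure is still recorded for these patients

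*Protocol*

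**What the plan says.** The Setting section gives two reasons for stopping study drug: intolerable side effects, and a lithium level above the therapeutic range. In either case, "The patient will subsequently be withdrawn from the study". The Risk Benefit Assessment repeats the rule: "The patient will be excluded from this study".

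The section on refusals, withdrawals and loss to follow-up adds investigator withdrawal: "Patients may be withdrawn if the investigator deems that it is detrimental or risky for the patient to continue". It then provides that "Follow up visits at endocrine clinic will be arranged for all withdrawn patients". It gives those visits no timing, no thyroid function test and no recording for the trial. It also says that withdrawn patients are not replaced.

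The primary outcome is fixed under Definition of cure: "Cure is defined as achievement of euthyroidism or hypothyroidism at 6 months after radioactive iodine therapy". It is read from TSH, free T4 and treatment status.

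Monitoring differs a little between arms. At week 1 the visit table has an entry for the lithium arm only: "Patients will be inquired of any possible side effects. 4mls blood will be drawn for lithium level and RP". The second lithium level is taken when radioactive iodine (RAI) is given: "Bloods will be drawn for TFT, RP, LFT and lithium level on the RAI day". Otherwise side effects are asked about equally, since of the standard adverse-event question the protocol says "This question will be put to the subject in his/her own language at each study visit".

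**The concern.** The trial asks whether cure at 6 months differs between the randomised groups. The withdrawal rule treats stopping a drug and leaving the study as one event. If cure status is then not recorded, the groups compared are those who tolerated their drug, not those randomised. A later analysis plan can choose an analysis set or a missing-data method, but it cannot supply outcomes that were never collected.

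Side effects can remove patients from either arm. A high lithium level can remove patients from the lithium arm only. Because one level check falls on the RAI day, the rule could remove a patient who has already completed two months of lithium.

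The direction of any bias is unknown. Patients taken off lithium might do worse if they return to an antithyroid drug, which the Background says lowers RAI efficacy. Patients flagged on the RAI day might do better, since the Background says lithium increases RAI retention.

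**Working it through.** **Text check**

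| Question | Where | Answer |
|---|---|---|
| Does stopping drug end participation? | Setting; Risk Benefit Assessment | Yes, stated twice |
| Are withdrawn patients seen again? | Refusals, withdrawals, lost to follow-up | Yes, at clinic visits with no schedule or test |
| Is month-6 cure recorded for them? | Setting; Definition of cure; Study Visits and Procedures | Not stated anywhere |

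**The plan's own sample size**

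With cure rates 0.91 and 0.57, two-sided alpha 0.05, power 0.90 and the protocol's rounded values: (1.96√0.385 + 1.29√0.327)² / 0.34² = 33.02, rounded up to 34. Allowing 20% dropout, 34/0.8 = 42.5, so 43 per arm. Both stated figures reproduce. The allowance protects the number of evaluable patients but not against selective loss.

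**Bias if removed patients are not observed**

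Inputs:
- 43 per arm (Sample size).
- The same true cure rate p in both arms: 0.57 (the carbimazole planning rate) or 0.72 (the Background's figure for cure within a year).
- k patients removed from an arm, so w = k/43, with cure rate q among them. Both k and q are assumptions; q was set at 0, 0.30, 0.57 and 1.

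Cure rate among those who stay = (p − wq)/(1 − w). The bias is this rate in the lithium arm minus this rate in the carbimazole arm.

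Examples with k = 4 in the lithium arm only (w = 0.093):
- p = 0.72, q = 0: 0.72/0.907 = 0.794, bias +0.074.
- p = 0.57, q = 1: (0.57 − 0.093)/0.907 = 0.526, bias −0.044.

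Rejection rates come from full binomial enumeration of the uncorrected Pearson chi-square test at 0.05. With no removals the rate is 0.053 (p = 0.57) or 0.052 (p = 0.72).

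| Removed: lithium / carbimazole | Bias, percentage points | False-positive rate |
|---|---|---|
| 1 / 0 | −1.0 to +1.7 | 0.049 to 0.054 |
| 2 / 0 | −2.1 to +3.5 | 0.051 to 0.064 |
| 4 / 0 | −4.4 to +7.4 | 0.048 to 0.118 |
| 2 / 1 | −1.1 to +1.8 | 0.047 to 0.054 |
| 4 / 2 | −2.3 to +3.9 | 0.052 to 0.069 |
| 4 / 4 | 0 | 0.051 to 0.053 |

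Rows with removals in both arms assume the same q in each. The positive extremes need q = 0 with p = 0.72. At q = 0.30 the false-positive rate is about 0.054 for 2/0 and 0.056 to 0.072 for 4/0. Losing 9 of 43 from lithium alone gives 0.099 to 0.563 at q = 0 to 0.30, but nothing in the protocol suggests losses on that scale.

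**Power if removed patients are kept**

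Arm rate = (1 − w) × planned rate + wq, with 43 per arm. Power with nobody affected is 0.970.

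| Affected: lithium / carbimazole | Kept, q = 0.57 | Kept, q = 0 | Removed (0.91 v 0.57) |
|---|---|---|---|
| 4 / 0 | 0.917 | 0.752 | 0.960 |
| 4 / 2 | 0.917 | 0.825 | 0.956 |
| 4 / 4 | 0.917 | 0.883 | 0.954 |

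**The case against.** The strongest reply is that the outcomes may exist anyway. The rule describes withdrawal by the investigator, not withdrawal of consent. This is a single-centre trial, clinic visits are promised to every withdrawn patient, the protocol calls its procedures routine, and cure needs only TSH, free T4 and treatment status. This stands in part: the text shows that collection is not stated, not that every outcome will be lost. But untimed visits without a specified test do not secure a month-6 result, and the rule as written puts the patient outside the study.

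The second reply is that removals will be few. The Background describes the lithium dose as very low and cites a study at a higher daily dose, over 21 days, without severe adverse effects. Setting also expects low risk. This also stands, although 21 days is shorter than two months. The rows with 4 removals are illustrations with no basis in the protocol, and their upper end needs no cures at all among those removed. The 0.72 is a within-one-year figure, not a 6-month one.

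The third reply is that an assessment for patients who never receive RAI goes beyond the definition of cure, which counts time from RAI. That is fair: such data would not by themselves say whether the patient counts as cured, so the analysis plan would have to.

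**Conclusion.** The concern holds. The protocol sets a rule under which drug stopping ends participation, and it does not secure the primary outcome afterwards. It should be fixed because the correction is cheap, not because large harm is likely. With 1 or 2 lithium-only removals, the bias is at most about 3.5 points in either direction and the false-positive rate stays near its nominal level. With 4 lithium-only removals, the worst case is 7.4 points and about 12%. Similar removals of like prognosis in both arms cause essentially no bias. These sizes rest on assumed removal counts and cure rates, on equal true cure in the two arms, and on the removed patients' outcomes not being recorded. The reading of the text is firm; the size and direction of the effect are not known.

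**What to change.** Leave the clinical stopping rule as it is and change only what follows for data collection.

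- **Setting and Risk Benefit Assessment:** replace withdrawal or exclusion from the study with a statement that study drug is stopped and the patient stays in the study for outcome collection.
- **If RAI is given, even late:** record thyroid function at months 1, 3 and 6, and cure status at month 6, counted from the actual RAI date.
- **If RAI is not given:** record thyroid function and treatment status at a stated time from randomisation, for example 8 months, the planned participation under Study Duration and Timeline. The analysis plan should say how these patients count.
- **Refusals, withdrawals, lost to follow-up:** state that investigator withdrawal ends study drug, and that only withdrawal of consent ends data collection.
- **Study Visits and Procedures:** add the assessment for patients without RAI.

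The analysis set can be left to the analysis plan once these data are collected.

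The cost is mostly wording. The budget lists 430 thyroid function tests, and 430/86 = 5 per patient: recruitment, RAI day, and months 1, 3 and 6. Little or no extra test cost follows. The statistical cost is possible loss of power. At the planned rates, keeping 4 affected lithium patients gives 92% if 57% of them are cured and 75% if none are, against 96% if they are removed. That loss reflects a smaller effect among all randomised patients, which removing them would hide.

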### Study Population

All adult patients who are 18 years and above with hyperthyroidism either newly diagnosed or relapse disease secondary to Graves' Disease, toxic multinodular goitre and toxic adenoma who are planned for radioactive iodine therapy as a definitive treatment will be included in this study.

The study period is from 18/12/2020 till 31/12/2021 at Pusat Perubatan Universiti Kebangsaan Malaysia.

## Inclusion Criteria

- Adult patients aged 18 years old and above with thyrotoxicosis who have been planned for definitive RAI:
  - consented for radioactive therapy as a definitive treatment.
  - able to comply with requirement of radioiodine therapy.
  - FT4 level below 40pmol/L

## Exclusion Criteria

- Pregnancy or Lactating mother
- Moderate to severe and active thyroid eye disease based on EUGOGO criteria, requires steroid cover
- Renal impairment, egfr <45ml/min (stage 3b)
- Underlying active malignancy
- Patients on medications that may interact with lithium (refer to **APPENDIX 1**)
- Patients on medications that may interfere with RAI effectiveness:
  - Amiodarone
  - Less than a month intravenous contrast
- Previous RAI < 6months
- Previous history of adverse effect following exposure to lithium or carbimazole.
- Thyroid carcinoma

## Refusals, withdrawals, lost to follow-up

Patients can withdraw themselves from the study at any point of time. If patient had changed the decision and opted out of radioactive iodine, endocrinologist should be contacted immediately and clinic visits will be arranged to review the patient. If patients were lost to follow-up, weekly phone calls will be made on 4 consecutive weeks. Patients may be withdrawn if the investigator deems that it is detrimental or risky for the patient to continue. Follow up visits at endocrine clinic will be arranged for all withdrawn patients. Withdrawn subjects will not be replaced

## Adverse Events

### **Definition:**

#### *Adverse event (AE)*

Any untoward medical occurrence in a subject administered an investigational intervention and which does not necessarily have a causal relationship with treatment.

An AE includes:

- A clinically significant worsening of a concomitant illness
- A clinical laboratory adverse event: a clinical laboratory abnormality which is clinically significant, i.e an abnormality that suggests a disease and/or organ toxicity and is of a severity that requires active management, Active management includes active treatment or further investigations, for example change of medicine dose or more frequent follow-up due to the abnormality.

In this trial, the following should be reported as AE:

- Treatment emergent symptoms which include:
  - Medical conditions or signs or symptoms that was absent before starting study treatment.
  - Medical conditions or signs or symptoms present before starting study treatment and worsen (increase severity or frequency) after starting study treatment.
- Abnormal laboratory values or tests that induce clinical signs or symptoms or require therapy.
- Any adverse experience even if no drug has been administered, for example during run in or wash out phase of the study.
- Any doubtful event should be treated as an AE.

#### *Unexpected adverse event*

Any adverse event not reported in the safety section of the Investigator's Brochure or if the event is of greater frequency, specificity or severity.

#### *Serious adverse event (SAE)*

Any adverse event occurring that:

- Results in death
- Is a life threatening adverse experience defined as any adverse event that places the subject, in the view of the investigator, at immediate risk of death from the reaction as it occurred. Note that this does not include a reaction that had it occurred in a more severe form, it would have caused death.
- Results in subject hospitalisation or prolongation of existing hospitalisation.

The following hospitalisations are not considered to be SAEs:

- Those planned before entry into the study.
- Elective treatment for a condition unrelated to study indication or study treatment
- Occur on an emergency outpatient basis and do not result in admission (unless fulfilling other criteria in SAE definition)
- Part of normal treatment or monitoring of the study indication and are not associated with any deterioration in condition.
- Results in a significant or persistent disability or incapacity defined as any event that results in a substantial and/or permanent disruption of the subject's ability to carry out normal life functions.
- Is any instance of overdose, either accidental or intentional (suspected or confirmed)
- Is any other important medical event, based upon appropriate medical judgement, that may jeopardise the subject or may require medical or surgical intervention to prevent or avert one of the outcomes listed above.

#### **Detecting and documenting AE**

- Information about all AEs, whether volunteered by the patient, discovered by investigator questioning or detected through physical examination, laboratory test or other means, would be documented on the Adverse Event Form and followed up as appropriate. The AE form should be emailed to the coordinating investigator [name] [name] at [contact].

- When eliciting experiences of AE from a subject, ask a standard non-leading question like "Do you feel different in any way since starting the new treatment/the last visit?" This question will be put to the subject in his/her own language at each study visit.

- Each AE should be described by:

Nature of AE

- This should be documented in terms of a medical diagnosis(es). When this is not possible, the AE should be documented in terms of signs and/or symptoms observed by the investigator or reported by the subject.

Duration:

- Start and end dates

Assessment of causality:

The investigator should attempt to explain each AE and assess its relationship, if any, to the study treatment. Causality should be assessed using the following definitions:

- Very likely
  - The AE follows a reasonable temporal sequence from study treatment administration
  - Abates upon discontinuation of study treatment
  - Reappears on repeated exposure (re-challenge)
- Probable
  - The AE follows a reasonable temporal sequence from study treatment administration
  - Abates upon discontinuation of study treatment
  - Cannot reasonably be explained by known characteristics of the subject's clinical state
- Possible
  - The AE follows a reasonable temporal sequence from study treatment administration.
  - But could have been produced by the subject's clinical state or other mode of therapy administered to the subject
- Doubtful
  - The temporal association between study treatment and AE is such that the study treatment is not likely to have any reasonable association with the observed event
- Very unlikely
  - The AE is definitely produced by the subject's clinical state or other mode of therapy administered to the subject

The degree of certainty with which an AE is attributed to study treatment or alternative cause like natural history of disease or concomitant treatment should be guided by the following considerations:

- Time relationship between treatment and occurrence of AE
- De-challenge and re-challenge information, if applicable
- Known pharmacology of the drug
- Dose response relationships
- Lack of alternative explanations i.e. no concomitant drug used and no other inter-current disease
- Reaction of similar nature being previously observed with this drug or class of drug
- Reaction having often been reported in literature for similar drug

### Severity of AE

- Mild: awareness of signs or symptoms, but they are easily tolerated
- Moderate: enough discomfort to cause interference with usual activity
- Severe: incapacitating, with inability to work or do usual activity.

Note that a severe AE is not necessarily serious. The term severe is a measure of the intensity while a serious AE is determined based on regulatory criteria. A life threatening AE is an SAE.

